- 11. Subjects with any known hypersensitivity to Kybella (deoxycholic acid) or any of the inactive ingredients: benzyl alcohol, dibasic sodium phosphate, sodium chloride, sodium hydroxide, hydrochloric acid
 - B. Source of subjects and recruitment methods
 Subjects will be recruited by flyers and handouts placed in the UCSD Dermatology
 clinic. Eligible patients will be determined from the inclusion and exclusion criteria.
 Eligible patients will be informed of the proposed study and its purpose and given the
 opportunity to ask any questions.

Standard HIPAA authorization to collect research data from the subject's medical record will be obtained at the time of informed consent.

C. Equitable Selection of Subjects

The risks and benefits of the research are fairly distributed among the populations that stand to benefit from it. Although the risk of this study is minimal, to be prudent, pregnant women will be excluded because of the potential harm posed to the fetus.

IV. Subject Enrollment

A. Number of subjects

15 subjects will be enrolled in the study.

B. Methods of enrollment

Subjects interested in participating in the study may contact one of the investigators. The study objectives, inclusion and exclusion criteria, possible risks and benefits of the study, and the information included in the informed consent form shall be discussed with prospective study participants. Subjects who believe they meet the exclusion and inclusion criteria and remain interested in the study shall be invited to come in for their screening visit. During the screening visit, the investigator will interview the subject and perform a simple clinical examination, particularly examining the thighs. Following the investigator's determination that the inclusion and exclusion criteria are met, the subject be invited to participate in the study.

C. Procedures for obtaining informed consent

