- 5. Thigh circumference measurement will be obtained with anthropometric tape measure.
 - Thigh circumference will be measured at site of maximum bulge at Screening.
 Vertical distance of this site from the floor will be measured, such that thigh circumference measurements at all following study assessments are performed at the same site.
- 6. Caliper measurement of inner thigh skin-fold thickness will be obtained.

Caliper measurement will be performed at site of maximum bulge at Screening.
 Vertical distance of this site from the floor will be measured, such that caliper measurements at all following study assessments are performed at the same site.

- 7. Thigh gap measurement will be obtained.
 - Patient will be asked to stand with legs at a fixed distance apart. Measurement
 will be performed between sites of maximum bulge at Screening. Vertical
 distance of these sites from the floor will be measured, such that thigh gap
 measurements at all following study assessments are performed at the same sites.
- 8. Pre-treatment photographs will be taken.
 - Patients will be asked to stand with feet apart at a uniform distance.

 Anteroposterior and posteroanterior photos will be taken.

Treatment:

9. Deoxycholic acid (Kybella) 10 mg/ mL will be injected subcutaneously, targeting the medial thigh deep fat compartment (pre-fascial). Subjects will receive deoxycholic acid 2 mg/ cm2, with injections of 0.2 mL spaced evenly 1 cm apart within the treatment area. Bilateral thighs will be treated. Each treatment will consist of a maximum of 8 mL (40 injection sites) of the study drug, with a maximum of 4 mL (20 injection sites) of the study drug for each thigh. All treatments will be performed by a study physician.

Post-Treatment Phone Call #1 (Day 3)

Phone call expected to take 5-10 minutes.

1. Two days after treatment, patient will be called and asked to report adverse events since last treatment. All adverse events will be recorded.

Second treatment (+/-) (Day 36 to 50)

The treatment visit is expected to take approximately 1 hour.

Prior to Kybella treatment:

1. Patient will be asked to complete the Subject Self-Rating Scale, rated from 0 to 6.

- 2. Patient's weight will be obtained.
- 3. Concomitant medications and procedures will be confirmed and recorded.
- 4. Adverse events will be recorded.
- 5. The investigator will perform a relevant physical examination.
- 6. Thigh circumference measurement will be obtained with anthropometric tape measure.

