 distance of these sites from the floor will be measured, such that thigh gap
 measurements at all following study assessments are performed at the same sites.
- 10. Follow-up photographs will be taken.
 - Patients will be asked to stand with feet apart at a uniform distance.
 Anteroposterior and posteroanterior photos will be taken.

b) Drugs to be used

Deoxycholic acid (Kybella) 10 mg/ mL will be injected subcutaneously, targeting the medial thigh deep fat compartment (pre-fascial).

c) Data to be collected and when data is to be collected

Data to be collected throughout the study includes the items listed in Schedule of Events.

VI. Biostatistical Analysis

A. Study endpoints

1. Primary Endpoint:

The primary endpoint will be safety endpoint, as defined by the incidence rate of patients who experience:

- a) Any adverse event (AE) ascertained by patient report or physician evaluation
- b) One or more serious adverse events (SAE) as defined by CTCAEv4
- c) Adverse events leading to study drug discontinuation.

2. Secondary Endpoints:

- a) Efficacy, defined as reduction in inner thigh fat, measured as follows:
 - i. Change in thigh circumference, as recorded with anthropometric tape measure.
 - Thigh circumference will be measured at site of maximum bulge at Screening. Vertical distance of this site from the floor will be measured, such that thigh circumference measurements at all following study assessments are performed at the same site.
 - ii. Change in inner thigh skin-fold thickness, as measured by calipers
 - Caliper measurement will be performed at site of maximum bulge at Screening. Vertical distance of this site from the floor will be measured, such that caliper measurements at all following study assessments are performed at the same site.
 - iii. Increase in "thigh gap," measured with patient standing with legs at a fixed distance apart. Measurement will be performed between sites of maximum bulge at Screening. Vertical distance of these sites from the floor will be measured, such that thigh gap

measurements at all following study assessments are performed at the same sites.

- iv. Percent accuracy by three blinded physicians in correctly identifying baseline photographs, upon independent review of before-and-after clinical photographs of the treatment area.
- Patients will be asked to stand with feet apart at a uniform distance.

 Anteroposterior and posteroanterior photos will be taken.

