- b) Patient satisfaction related to study treatment:
 - i. Improvement in patient satisfaction, as measured by
 Subject Self-Rating Scale, a 0 (extremely dissatisfied) to 6
 (extremely satisfied) scale
 - ii. Scores on additional post-treatment patient satisfaction questionnaire

B. Statistical methods

This is a small descriptive study, with the primary safety endpoint of the incidence rate of patients who experience:

- 1) Any adverse event (AE) ascertained by patient report, physician evaluation, or laboratory value
- 2) One or more serious adverse events (SAE) as defined by CTCAEv4
- 3) Adverse events leading to study drug discontinuation.

The safety analysis will be based on the safety population, which is defined as all patients who have received at least one dose of study medication and who have had at least one post-baseline safety evaluation.

Adverse events will be explored for trends.

The efficacy analysis will be based on the intent-to-treat (ITT) population. In the ITT population, patients will be counted in the treatment group upon informed consent and completion of Baseline measurements, regardless of receiving any dose of study medication.

In the case of a subject's early termination from study, missing values will be imputed using last observation carried forward (LOCF) method.

Baseline values will be those values measured on day of screening, which may be combined with Day 1.

Reduction in inner thigh fat, as measured by tape measure and calipers, will be presented as change in millimeters or centimeters, and presented descriptively. Percent accuracy by three independent blinded physicians in correctly identifying baseline photographs, when comparing before-and-after clinical photographs of the treatment area, will be reported. Patient satisfaction scores on Subject Self-Rating scale and post-treatment patient satisfaction questionnaire will be presented descriptively.

VII. Risks and Discomforts

A. Complications of treatment procedure/drug side effects and toxicities

Deoxycholic acid will be injected subcutaneously in the treatment area by the principal investigator [name], or by a member of the study team who is a UCSD Dermatology resident physician, under direction of [name].

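### The safety population that carries the primary endpoint leaves out any injected subject with no later safety information, instead of counting everyone injected

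*Combined protocol and SAP*

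**What the plan says.** Section VI.A makes safety the primary endpoint: "The primary endpoint will be safety endpoint, as defined by the incidence rate of patients who experience" any adverse event, a serious adverse event, or (component c) "Adverse events leading to study drug discontinuation". Section VI.B assigns the analysis set: "The safety analysis will be based on the safety population". It defines that set by two conditions joined by 'and': "all patients who have received at least one dose of study medication", and "who have had at least one post-baseline safety evaluation". What counts as a post-baseline safety evaluation is not defined. Baseline is the screening day, which may or may not be the day of the first injection.

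In section V.a the steps for the first treatment visit end with the injection. The first listed collection of adverse events after it is the Day 3 call: "Two days after treatment, patient will be called and asked to report adverse events since last treatment". Adverse events are recorded again before each later treatment and at the Week 4 and Week 12 follow-ups. Sections X.B and XI add that investigators collect safety data at every visit, and that events are reviewed when they occur and filed in the subject's binder.

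Section IV.A gives the size: "15 subjects will be enrolled in the study".

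**The concern.** The second condition removes an injected subject from both numerator and denominator when no safety information follows the injection. Section IV.C allows withdrawal at any time, so this can happen before the Day 3 call. Loss straight after an injection is not obviously unrelated to the outcome: a subject who breaks off contact may have done so because of an adverse event, which is what component (c) counts. If so, the exclusion is informative.

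Nothing else in the plan brings such a subject back. Last observation carried forward fills missing values but does not change who belongs to a population. The intent-to-treat set keeps subjects "regardless of receiving any dose of study medication", but it serves efficacy only.

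What is at stake is the count for the rare components. In a 15-subject study of a treatment area with no earlier reports for this drug alone, none and one read differently in a safety summary.

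**Working it through.** There is no plan figure to reproduce. The enrolment of 15 comes without a power or precision calculation, and the analysis is descriptive.

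**Step 1. Who is actually excluded?**

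- *Reaction seen or reported on Day 1.* VI.A accepts patient report or physician evaluation, a study physician gives the injections, X.B has safety data collected at each visit, and XI has events documented. This would most naturally count as an evaluation, so the subject stays in.
- *Day 3 call missed, later visit attended.* Adverse events are recorded at that visit. The subject stays in.
- *No safety information of any kind after the injection.* The subject is excluded.

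The undefined term adds some noise. A subject screened on an earlier day has a pre-injection physical examination on Day 1 that falls after baseline, and someone could count it. A subject screened and injected on the same day has no such examination. Membership should not depend on that.

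**Step 2. Which way does the exclusion move the rate?** Let N be the number injected, k the number injected with no later safety information, x the events known among the other N − k, and j the events among the k, which are unknown (0 ≤ j ≤ k).

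- Plan: x/(N − k)
- Truth: (x + j)/N, between x/N and (x + k)/N

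The plan's figure always lies between these bounds. It is at least x/N because its denominator is smaller. It is at most (x + k)/N because (x + k)(N − k) − xN = k(N − k − x) ≥ 0. It is therefore too high if the lost subjects had no event, and too low (or, at 100%, equal) if all of them had one.

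**Step 3. Numbers.** Assumptions: all 15 enrolled are injected (N = 15), and k = 1 unless stated. Intervals are exact (Clopper-Pearson) 95%.

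| Known events x | Plan | Truth if lost subject(s) had no event | Truth if lost subject(s) had the event |
|---|---|---|---|
| 0 | 0/14 = 0% (0 to 23.2%) | 0/15 = 0% | 1/15 = 6.7% (0.2 to 31.9%) |
| 1 | 1/14 = 7.1% (0.2 to 33.9%) | 1/15 = 6.7% (0.2 to 31.9%) | 2/15 = 13.3% (1.7 to 40.5%) |
| 8 | 8/14 = 57.1% | 8/15 = 53.3% | 9/15 = 60.0% |
| 11 | 11/14 = 78.6% | 11/15 = 73.3% | 12/15 = 80.0% |
| 0, k = 2 | 0/13 = 0% | 0/15 = 0% | 2/15 = 13.3% |
| 0, k = 3 | 0/12 = 0% (0 to 26.5%) | 0/15 = 0% | 3/15 = 20.0% (4.3 to 48.1%) |

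The upper limit for 0/14 is 1 − 0.025^(1/14) = 0.232. The lower limit for 1/15 is 1 − 0.975^(1/15) = 0.002, and its upper limit is the 97.5% quantile of a Beta(2, 14) distribution, 0.319.

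The rows with x = 0 or 1 stand for serious or discontinuation events, where one subject decides between none and one. The rows with x = 8 or 11 stand for any adverse event, which shifts by about 1 to 5 percentage points.

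**The case against.** The strongest reply is that the plan already covers the case that matters. A reader might infer that a subject who reacts on Day 1 and withdraws disappears from the primary endpoint. The documents do not support that. X.B and XI have safety data collected at each visit and events documented as they arise, and VI.A accepts either patient report or physician evaluation. A reaction that anyone saw or was told about would probably keep the subject in. Nor does a missed Day 3 call exclude anyone by itself, since later visits record adverse events too. This part of the reply stands, and it narrows the point to subjects with no post-injection information at all.

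A second reply is that no event is known for such a subject, so a larger denominator recovers nothing. That is true. The gain is that the unknown becomes visible instead of being dropped silently.

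Third, one might infer that the exclusion can only hide events. That is wrong for the reported rate: as step 2 shows, dropping an event-free subject raises it.

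Fourth, the contrast with the intent-to-treat set proves nothing by itself. That set serves efficacy and does not show the safety set to be wrong.

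Finally, V.c refers to a Schedule of Events that is not in the text available here. If it already lists an adverse event entry after the injection, that part of the fix is met. The wording of VI.B would still need the change.

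**Conclusion.** The point holds in a limited form. VI.B states a rule, not a mere omission: an injected subject with no later safety evaluation leaves the primary analysis, and the qualifying term is undefined. The number affected is probably 0 or 1 of 15. That is a judgement, because the documents give no early-loss rate; the table shows up to 3.

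The direction of the bias depends on an outcome nobody would know. The worst case for one subject is 0/14 (0%) reported where 1/15 (6.7%) is true. It requires a discontinuation event that nobody recorded, in a subject never contacted again. The intervals, 0 to 23.2% and 0.2 to 31.9%, overlap heavily, and no test or threshold in this descriptive study depends on the difference. The stronger claim, that the plan loses Day 1 reactions as a matter of course, is not supported. This is a low-priority improvement, worth making because it removes a possible informative exclusion from the primary endpoint at almost no cost.

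**What to change.** In VI.B, define the safety population as all subjects who received at least one injection, and delete the second condition. Report the number with no safety information after their first injection. If that number is above zero, give each primary incidence twice over the full injected denominator: once with these subjects counted as no event, and once as event. With one such subject and no known discontinuation event, the report would read 0/15 to 1/15 (0% to 6.7%) in place of 0/14.

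In V.a, list the adverse event recording that X.B already promises as a step after the injection at each treatment visit. For population membership this matters only at the first treatment, because later treatment visits already record adverse events before the injection. At those visits the step simply makes the record complete.

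The cost is about one sentence in VI.B and one line in the visit procedures. The downside is two figures per component, and only if someone has no post-injection information.

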There will be no randomization. Study participants will be treated with deoxycholic acid (Kybella) 10 mg/ mL injected subcutaneously, targeting the medial thigh deep fat compartment (pre-fascial). Subjects will receive deoxycholic acid 2 mg/ cm², with injections of 0.2 mL spaced evenly 1 cm apart within the treatment area. Bilateral upper inner thighs will be treated. Each treatment will consist of a maximum of 8 mL (40 injection sites) of the study drug, with a maximum of 4 mL (20 injection sites) of the study drug for each thigh. All treatments will be performed by a study physician. Subjects will receive 1 to 4 treatment sessions, each spaced 6 weeks +/- 1 week. Treatment #2, #3, or #4 will be pursued if patient desires more treatment, and if there is sufficient fat for treatment, per investigator's judgment.

V. Study Procedures

a) Study visits and parameters to be measured
 All visits in this study will be performed at the UCSD Dermatology Clinic, 3rd floor,
 [name].

Screening/Baseline Visit (Visit 1, Day -14 to 1)

This visit is expected to take approximately 1 hour. The following describes the procedures performed at this visit.

Prior to any screening assessments, informed consent will be obtained by the
investigator. When the subject fully understands the nature of the study and its risks,
the subject will be asked to sign and date the informed consent form. The
investigator will then sign and date the form.

- 2. A detailed medical history of information pertaining to treatment will be obtained.
- 3. The investigator will perform a relevant physical examination.
- 4. Patient's weight will be obtained.
- 5. The subject will be asked to complete the Subject Self-Rating Scale (0 to 6 scale).
- 6. If the subject meets the criteria for the study, the subject will be assigned the next consecutive subject number.
- 7. Females of childbearing age will undergo a urine pregnancy test
- 8. The investigator will determine the patient's eligibility for the study.

First treatment (Visit 2, Day 1)

The treatment visit is expected to take approximately 1 hour. The first treatment may be combined with Screening/ Baseline.

Prior to Kybella treatment:

- 1. Patient will be asked to complete the Subject Self-Rating Scale, rated from 0 to 6.
- 2. Patient's weight will be obtained.
- 3. Concomitant medications and procedures will be confirmed and recorded.
- 4. The investigator will perform a relevant physical examination.

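### With LOCF as the only missing-data rule and no post-baseline value required, a subject injected once and then lost can enter the efficacy summary as no thigh change

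*Combined protocol and SAP*

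**What the plan says.** Section VI.B (Statistical methods) places efficacy in an intent-to-treat population in which "patients will be counted in the treatment group upon informed consent and completion of Baseline measurements, regardless of receiving any dose of study medication". No post-baseline efficacy value is required. The safety population in the same section does require a dose and a later safety evaluation.

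The missing-data rule is one sentence: "In the case of a subject's early termination from study", "missing values will be imputed using last observation carried forward (LOCF) method". It covers early termination only, so a missed visit in a continuing subject has no rule. The plan asks for no observed-case result, no sensitivity analysis and no count of imputed values.

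On baseline, VI.B says "Baseline values will be those values measured on day of screening, which may be combined with Day 1". The Screening/Baseline list in section V.a schedules no tape, caliper or thigh-gap measurement. These first appear at Visit 2, before injection ("Thigh circumference measurement will be obtained with anthropometric tape measure").

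The study has one arm. Section IV.D states "There will be no randomization".

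**The concern.** The efficacy result is a descriptive change in each thigh measure. LOCF fills a gap with the last value available, and this schedule leaves a stretch after the first injection in which the last value available is the pre-injection one. A subject who leaves in that stretch has an unknown outcome, which the rule would report as no change. Later losses have a milder form of the same problem: a subject who leaves after a further injection and before the Week 4 visit carries a value taken before that injection.

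The reported figure could therefore mix measured outcomes with pre-injection values, and the reader would not be told how many of each there are. As no test is planned, the descriptive figure is the whole efficacy result.

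A separate and smaller matter is that the set admits subjects who were never injected. The usual reason for keeping untreated subjects is to preserve a randomised comparison, and there is none here. For thigh measures the case is narrow, because they are first listed at the visit where injection takes place.

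**Working it through.** **Inputs.** N = 15 (IV.A). Sessions are 6 weeks apart, plus or minus 1 week (IV.D). Thigh measures precede each injection and are repeated 4 and 12 weeks after the last treatment (V.a). No dropout rate, effect size or SD is given, so the plan has no figure on this point to reproduce.

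**Step 1: when is the first thigh value after injection 1?**
- If a second session follows: 1 + 42 − 7 = Day 36 to 1 + 42 + 7 = Day 50, which agrees with V.a. The gap is 35 to 49 days.
- If treatment stops after one session: 1 + 28 = Day 29, a gap of 28 days.
- The only scheduled contact in between is the phone call, which covers adverse events alone: "Two days after treatment, patient will be called and asked to report adverse events since last treatment".

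**Step 2: what does LOCF return for a subject lost in that gap?** Change = last observed value − baseline.
- One pre-injection value only (Screening combined with Day 1, or thighs measured on Day 1 only): baseline − baseline = 0.
- Visits split and both days measured: Day 1 − Screening, which is measurement noise and holds no post-treatment information.

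**Step 3: loss after a later injection and before Week 4.** The carried value was taken before the last injection. For a fourth session the Week 12 visit is 190 − 106 = 232 − 148 = 84 days after it.

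**Step 4: effect on the mean.** Let m be the mean change among the 15 − k subjects with a later value, and let the other k contribute zero. Reported mean = [(15 − k)m + k × 0]/15 = m(15 − k)/15.

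| k (assumed) | Factor | Reduction |
|---|---|---|
| 1 | 14/15 = 0.933 | 6.7% |
| 2 | 13/15 = 0.867 | 13.3% |
| 3 | 12/15 = 0.800 | 20.0% |

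**Step 5: how likely is k ≥ 1?** This depends on an assumed rate d of loss before any second measurement. Expected number = 15d; chance of at least one = 1 − (1 − d)^15.
- d = 5%: 0.75 expected, 54%.
- d = 10%: 1.5 expected, 79%.
- d = 20%: 3.0 expected, 96%.

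**Step 6: would a median escape this?** The plan names neither mean nor median. I simulated 15 − k normal changes with SD 1 plus k zeros (400,000 runs) and divided the average median of all 15 by the average median of the 15 − k.

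| Assumed mean change | k = 1 | k = 2 | k = 3 |
|---|---|---|---|
| 0.5 SD | 0.85 | 0.68 | 0.51 |
| 1 SD | 0.91 | 0.81 | 0.69 |
| 2 SD | 0.96 | 0.905 | 0.84 |
| 3 SD | 0.97 | 0.94 | 0.90 |

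The median also moves, by an amount that depends on the unknown effect.

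**The case against.** The strongest reply is that this is a small descriptive study with secondary efficacy endpoints. No test, error rate or decision rule is touched, and zeros err on the cautious side. All of that stands and limits the importance. It does not tell a reader how much of the reported change was measured.

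A second reply is that an observed-case figure can flatter the treatment. If subjects leave because of pain or lack of benefit, dropping them favours an open-label, single-arm result. This also stands, and it is a reason to keep LOCF beside the observed figure.

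Some stronger readings are tempting, but the documents do not support them:
- That the plan prescribes a zero. It does not say whether baseline may be carried, and the value need not be exactly zero if thighs are measured on both Screening and Day 1. The measurement notes refer to the site of maximum bulge at Screening, so a measurement that day is plausible although it is not listed.
- That admitting uninjected subjects causes the problem. The subject injected once and lost would be in an injected-only set too. The two matters are separate.
- That carrying Week 4 to Week 12 is an error. It is ordinary LOCF, and the value is post-treatment.
- That the low Self-Rating score required at entry caps a satisfied proportion. The plan names no such proportion, and the scale is repeated at Visit 2 before injection.

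**Conclusion.** The concern holds as a modest one. Applied literally, the stated rules can report a missing thigh outcome as no change or near-zero change. Each baseline-only subject in 15 who contributes zero takes 6.7% of m off the mean. The size rests on k, which is assumed; three such subjects would mean 20% lost before any second measurement, and nothing in the documents supports or excludes that. The direction is toward no effect, provided the subjects who were measured do show a reduction.

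A reader might infer that the plan exaggerates efficacy or that its main result is unsafe. Neither follows: baseline-only values understate a reduction, and the primary safety endpoint uses a different analysis population.

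**What to change.** In VI.B:

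1. Define the efficacy set as all subjects with at least one injection and a pre-injection baseline value. This removes never-injected subjects but does not by itself remove the zero for a subject injected once and lost, so item 2 is also needed.
2. For each thigh measure and the Self-Rating Scale, report the observed change at the Week 12 follow-up with its n. Show the LOCF result beside it, with the number of values imputed and how many of those are baseline carried forward.
3. Reconcile the screening-day baseline in VI.B with the thigh measures first listed at Visit 2 in V.a, so that one value per subject is named as baseline.

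The plan names no efficacy time point. Week 12 is suggested because it is the last scheduled visit.

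**Cost.** Analysis wording only, with no new visits or data. There will be two results per endpoint, and the observed n may fall below 15. The observed figure may be favourable if leaving is related to pain or lack of benefit, so neither result should be shown without the other.

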This prospective, open-label, single-arm, single-center clinical study at the University of California, San Diego Department of Dermatology is designed primarily to investigate the safety and efficacy of deoxycholic acid injection for the treatment of upper inner thigh fat. The secondary objective of this study is evaluation of patient-reported satisfaction outcomes after treatment of upper inner thigh fat with deoxycholic acid injection.

III. Subject Selection

A. Inclusion/Exclusion criteria

Inclusion

- 1. Adults aged 18 to 65
- 2. Discrete area of mild-to-moderate excess upper inner thigh fat, amenable to treatment at the discretion of the investigator
- 3. Subjects who score 0 (extremely dissatisfied) to 2 (slightly dissatisfied) on a Subject Self-Rating Scale, pertaining to upper inner thigh fat, with the scale ranging from 0 (extremely dissatisfied) to 6 (extremely satisfied)
- 4. Body mass index (BMI) less than 30 kg/m²
- 5. Stable body weight for previous 6 months (weight within 10 pounds of baseline)
- 6. Subjects must be in stable health, as confirmed by medical history, per investigator judgment
- 7. Subjects must be able to read, sign, and understand the informed consent
- 8. Subjects must we willing to avoid any other treatments to the inner thigh, including cryolipolysis and liposuction, during the study period.
- 9. Subjects must be willing to avoid changes in diet or exercise, any weight loss program, and any weight loss supplements, during the study period.
- 10. Subjects must be able and willing to avoid anticoagulation (aspirin, warfarin, hepain, rivaroxaban) for 1 week prior to each study treatment

Exclusion:

1. History of treatment for inner thigh fat, including cryolipolysis, noninvasive body contouring or liposuction in the last year

- 2. Previous trauma or surgery to pelvis or thighs
- 3. Subjects with an unstable medical condition, as deemed by the investigator
- 4. Women who are pregnant or lactating or plan to become pregnant during the study period
- 5. Lymphedema or edema of thigh
- 6. Excessive skin laxity in the treatment area, as judged by the investigator
- 7. Severe thigh cellulite
- 8. Subjects with any disease in the treatment area, such as dermatologic disease, that may be exacerbated by the study treatment
- 9. Subjects with any condition that may impair the evaluation of inner thigh fat
- 10. Subjects with known bleeding diathesis

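### For anyone screened before Day 1, the self-rating baseline is the entry score, so the reported improvement includes regression to the mean (minor)

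*Combined protocol and SAP*

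**What the plan says.** - **Baseline rule (VI.B):** "Baseline values will be those values measured on day of screening, which may be combined with Day 1".
- **Entry (III.A, inclusion criterion 3):** "Subjects who score 0 (extremely dissatisfied) to 2 (slightly dissatisfied) on a Subject Self-Rating Scale". The criterion concerns the upper inner thighs, on a scale from 0 to 6.
- **Visit 1 (V.a, Day -14 to 1):** the self-rating is item 5, and the eligibility decision is item 8 of the same list.
- **Visit 2 (V.a, Day 1), before injection, item 1:** "Patient will be asked to complete the Subject Self-Rating Scale, rated from 0 to 6". The Visit 2 list contains no eligibility item.
- **Combining the two visits is optional (V.a):** "The first treatment may be combined with Screening/ Baseline".
- **Endpoint (VI.A, secondary b.i):** improvement on this same scale. The study has one arm and no randomization (II.A, IV.D), 15 subjects (IV.A), and descriptive reporting (VI.B).

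**The concern.** Subjects enter because a single score is low. Part of a low score is temporary error, and a later score from the same person will on average be higher even if nothing has changed. If the low score is also the baseline, that rise is counted as improvement. The direction is known (towards benefit), and without a control arm nothing in the design separates it from a treatment effect. Descriptive reporting does not remove it, because the mean change being described is itself the biased quantity.

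At stake is one of six secondary measures: circumference, skin-fold, thigh gap, photograph accuracy, self-rating and questionnaire. The problem is avoidable, because a pre-injection score that was not used for selection is already scheduled.

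**Working it through.** **No plan figure to reproduce.** The documents give no mean, SD, reliability or power calculation for the self-rating, and the 15 subjects are not derived. All sizes below rest on assumptions.

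**Step 1: which score is the baseline?**

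| Case | Score used for entry | Baseline under VI.B | Other score before injection |
|---|---|---|---|
| Screened before Day 1 | Visit 1 | Visit 1 | Visit 2, not used as baseline |
| Screened and treated on Day 1 | Day 1 | Day 1 | Same day; may repeat the first |

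The avoidable bias is in the first row.

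**Step 2: approximate formula.** For a normal score with pool mean m, SD s and test-retest correlation ρ, selected at a rounded score of 2 or below (cut at 2.5), with no treatment effect:

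spurious gain ≈ (1 − ρ) × s × φ(c)/Φ(c), where c = (2.5 − m)/s.

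Example: m = 2.0, s = 1.5, ρ = 0.7.
- c = 0.5/1.5 = 0.333; φ(c) = 0.377; Φ(c) = 0.631.
- Gain ≈ 0.3 × 1.5 × 0.377/0.631 = 0.27.

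**Step 3: simulation on the 0 to 6 scale.** Scores are rounded and clipped, errors are independent between visits, selection is on a screening score of 2 or below, and there is no treatment effect. Selected scenarios:

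| m | s | ρ | Share qualifying | Formula | Simulated gain, screening baseline | Simulated gain, Visit 2 baseline | Standard error, n = 15 | Gain / standard error |
|---|---|---|---|---|---|---|---|---|
| 1.5 | 1.0 | 0.9 | 0.84 | 0.03 | 0.05 | 0.000 | 0.15 | 0.05/0.15 = 0.33 |
| 1.5 | 1.5 | 0.7 | 0.75 | 0.19 | 0.22 | 0.000 | 0.26 | 0.22/0.26 = 0.85 |
| 2.0 | 1.5 | 0.7 | 0.63 | 0.27 | 0.30 | -0.002 | 0.27 | 0.30/0.27 = 1.11 |
| 3.0 | 1.5 | 0.7 | 0.37 | 0.46 | 0.52 | 0.001 | 0.29 | 0.52/0.29 = 1.79 |

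**Step 4: full grid.** Means 1, 1.5, 2, 2.5 and 3; SDs 1.0, 1.25 and 1.5; reliability 0.6, 0.7, 0.8 and 0.9: 5 × 3 × 4 = 60 scenarios.
- Screening baseline: gain 0.025 to 0.671, median 0.200.
- Separate-day Visit 2 baseline: -0.004 to 0.004.
- In the 20 scenarios where at least 75% qualify: 0.025 to 0.209, median 0.090, which is 0.18 to 0.80 of the standard error at n = 15. All 20 have an assumed pool mean of 1 or 1.5.

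**Step 5: what remains after the fix** (within scenarios where at least 75% qualify).
- Half the subjects screened and treated on the same day: 0.5 × 0.025 = 0.013 to 0.5 × 0.209 = 0.104.
- Separate days, but the two pre-injection scores share short-term error (their correlation of 0.7 to 0.9 exceeds the 0.6 to 0.8 with follow-up): 0.013 to 0.139 remains, and 32% to 81% of the bias is removed.

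**The case against.** **The effect is small and conditional.** It needs separate days, the plan allows the visits to be combined, and the number of such subjects is unknown. The endpoint is secondary, with no test or threshold, and VI.B says the self-rating scores will be presented descriptively, so nothing stops the Visit 2 score being shown. This stands as a limit on weight. It does not remove the point: the endpoint is worded as improvement, and the stated rule fixes what that improvement is measured from.

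**The fix does not make the result attributable to treatment.** True: with one arm, no choice of baseline does that. The fix removes one avoidable bias of known direction, and only partly in the two situations of Step 5.

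**A reader might infer that the thigh and photograph endpoints have no baseline.** The Visit 1 list has no tape, caliper, thigh-gap or photograph item; these first appear at Visit 2 before injection. The documents do not support going further. Visit 2 holds the first listed values, all before injection, so no change in results is expected. The wording "Thigh circumference will be measured at site of maximum bulge at Screening" may fix only the site, or may imply a screening measurement. Section V.c also says "Data to be collected throughout the study includes the items listed in Schedule of Events", and that schedule is not in the text available for this review; it may settle the matter.

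**A reader might infer which photographs enter the comparison.** VI.A speaks only of the readers' task "upon independent review of before-and-after clinical photographs of the treatment area". It does not say which later photographs count as after, and no claim is made here.

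**Conclusion.** The point holds for the self-rating and is minor. For subjects screened before Day 1, the rule makes the entry score the baseline, and the reported improvement is biased upward.

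The size is not fixed by the documents. Under the stated assumptions it is 0.03 to 0.67 points, on a scale whose adjacent answers differ by 1 point. The narrower 0.03 to 0.21 should not be read as the expected size: it applies only if most people screened already score 0 to 2. Section IV.B makes that plausible, since people who believe they qualify are invited, but does not establish it. The near-zero bias with a Visit 2 baseline assumes separate days, independent errors and no second selection at Visit 2.

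The primary safety endpoint is unaffected. A reader might also assume that moving the baseline leaves the ITT population untouched. That is not automatic: VI.B ties ITT entry to completed baseline measurements, so the rewording must settle it.

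**What to change.** Replace the baseline sentence in VI.B with:

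*Baseline is the last value recorded before the first injection (normally Visit 2, Day 1). The screening self-rating is used for eligibility only, except that for a subject who is never injected baseline is the last value recorded at Visit 1 or Visit 2.*

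If the visits are combined and the scale is completed once, say that this score serves both purposes.

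Add to the ITT definition, so that membership does not shift:

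*For ITT entry, baseline measurements are complete when the Screening/Baseline Visit (Visit 1) assessments are complete.*

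In the report, give the number of subjects screened and treated on the same day. State that regression to the mean may remain for them and, if the two pre-injection scores share short-term error, partly for the others.

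As a consistency check only, compare the Visit 1 list and the Schedule of Events with the new rule for the tape, caliper, thigh-gap and photograph items.

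**Cost:** two sentences of rewording and no new data. The reported improvement may be slightly smaller, and some Visit 2 baseline scores may lie above the entry limit of 2.
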